3.3 Exploratory data

Exploratory data variables will be measured at baseline and at days 3,5 and 8 (Tables 9, 11). Differences in exploratory variables will be calculated for each patient, enabling an estimate of the mean difference and 95% confidence interval to be calculated for each treatment arm. The differences for the treatment groups will be compared using parametric or non-parametric tests as appropriate.

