3. STUDY DESIGN

The proposed study will be run as a double-blind, randomized controlled experimental medicine study in male and female hospitalised patients (n=60) aged 18 or over, with confirmed COVID-19 infection. Patients who are admitted with confirmed COVID-19 infection will be screened with a routine medical assessment (see Table 1) and enrolled if they meet the eligibility criteria. Subjects will be block randomised based on age to continuous intravenous infusion of placebo or TRV027 for 7 days.

Day 1 procedures can occur on the same day of screening and include a venous blood test prior to commencing an intravenous infusion of either placebo (250ml sodium chloride 0.9%) or TRV027 in 250ml sodium chloride 0.9% at 12mg/hr. The infusions will continue for 7 days. Venous blood tests will be repeated at days 3, 5 and 8 amounting to approximately 120mLs of blood in total over the 8-day period.

Once the infusion has finished, the subjects will remain in hospital for a further 24 hours for vital signs and adverse event monitoring. If the infusion is stopped before the 7-day dosing period finishes, they will be advised to remain in hospital for a 24-hour period for monitoring during which time the study assessments will continue. If discharge is planned for day 6 or 7 the day 8 blood tests can be taken on the day of discharge. They will also be followed up at Day 30 either by telephone call or through examination of medical records.

Table 1: Schedule of Study Events

Study Day	*Screening	*1	2	3	4	5	6	7	8	9	30
Informed consent (or agreement from consultee if incapacitated)	X										
Eligibility assessment; routine medical assessment (history, observations)	X										
Review of Concomitant Medications ¹		X	X	X	X	X	X	X	X		
Pregnancy test (If appropriate)	X										
Venous blood test for primary and exploratory endpoint assessment:											
D-dimer		X		X		X			X		
Platelets		X		X		X			X		
aPTT		X		X		X			X		
INR		X		X		X			X		
Fibrinogen		X		X		X			X		
Plasma Renin Mass		X									
Total Bilirubin		X		X		X			X		
LDH		X		X		X			X		
Haptoglobin		X		X		X			X		
Creatinine		X		X		X			X		
BNP		X		X		X			X		
Troponin		X		X		X			X		
Ferritin		X		X		X			X		
Pro-calcitonin		X		X		X			X		
Glucose		X		X		X			X		
Clinical assessment for exploratory endpoints											
Inotrope requirement		X		X		X			X		
GCS		X		X		X			X		
SOFA score		X		X		X			X		
Randomisation		X									
Infusion		X	X	X	X	X	X	X	X		
Vital signs monitoring four times a day		X	X	X	X	X	X	X	X	X	

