7. STATISTICS AND DATA ANALYSIS

This sample size (30 each group) provides 80% power (alpha 0.05) to detect a 30% change in D-dimer. Subjects will be block randomised based on age (<60, 60-69, >69 years) using a code generated by the trial statistician.

Mean change from baseline D-dimer at day 1-3 post randomisation (and exploratory variables) will be compared using paired or unpaired non-parametric methods as appropriate. The relationship between change from baseline and pre-treatment plasma renin will be investigated, on the basis that subjects with low renin (and hence greater RAS activation) would be predicted to have the greater response.

The aim of this study is to understand the relationship between the RAS, coagulopathy, and COVID-19. The results of this study have potential implications for studies which are currently being planned using RAS modulators (including TRV027) in COVID-19. Design decisions for these study need to be taken before this study will fully recruit. Hence, unblinded aggregate data, for those patients who have completed the dosing period, will be reviewed by the study team to help guide the design of these studies. Individual unblinded data will not be reviewed.

Data and all appropriate documentation will be stored for a minimum of 10 years after the completion of the study, including the follow-up period.

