1.3 Study Endpoints

Primary endpoint

Mean change from baseline D-dimer at day 1 to day 3 post randomisation will be compared using paired or unpaired non-parametric methods as appropriate.

Secondary endpoints

Mean change from baseline to day 1 plasma renin and from day 1 to day 3, day 5, day 8 for exploratory variables will be investigated

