1.5 Study sample size

The sample size (30 each group) provides 80% power (alpha 0.05) to detect a 30% reduction in the D-dimer level. Subjects will be block randomised based on age (<60, 60-69, >69 years).

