3.7 Additional data

Vital signs and cardiovascular monitoring will be documented at days 1, 3 and 5. (Table 12).

Table 1. Baseline characteristics

	FAS		IAS	
	Control	TRV027	Control	TRV027
	Median (range) or N (%)			
Age (yr)				
Age group				
<60				
60-69				
>69				
Gender				
Male				
Female				
BMI (kg/m²)				
Ethnicity				
White				
Mixed				
Asian				
Black				
Other				
Disease severity?				
Ie FDA grade 1-5?				

Table 2 Drug Compliance

	Control N (%)	TRV027 N (%)
Total Missed doses		
Total % Compliance		
Median missed doses per patient (range)		
Patients with missed dose due to hospital discharge		
Patients with missed dose due to death		

Table 3 Safety data – Pooled Adverse events

	Control		TRV-027	
	No. of Events	No. of Subjects*	No. of Events	No. of Subjects*
Number of Adverse events				
Severity				
Grade 1				
Grade 2				
Grade 3				
Grade 4				
Grade 5				
Missing				
AE classification				
Not serious				
Serious				
AE expectedness				
Expected				
Unexpected				
Not Applicable				
Missing				
Relation to study				
Definitely				
Probably				
Possibly				
Unlikely				
Not related				
Not assessable				
Missing				

* A patient may have several AEs

Table 4 – TRV027 Safety data –Adverse events details by patient

Control				TRV-027			
Pt ID	AE category	AE name	Grade	Pt ID	AE category	AE name	Grade

Table 6 Safety data – Serious Adverse Events

	Control		TRV027	
	No. of Events	No. of Subjects	No. of Events	No. of Subjects
Number of Serious Adverse Events				
Reasons for SAE				
Resulted in death				
Life threatening				
Congenital anomaly/birth defect				
Persistent or significant				
Disability/incapacity				
Inpatient hospitalisation/prolongation of existing				
Other				
Severity				
Mild				
Moderate				
Severe				
Life threatening				
Death				
Causal relationship to study drug				
Definitely				
Probably				
Possibly				
Unlikely				
Not related				
Not assessable				

Table 7 Safety data – Serious Adverse events details (Controls)

SAE description	SAE Term	Outcome

Table 8 Safety data – Serious Adverse events details (TRV027)

SAE description	SAE Term	Outcome

Table 9 Day 30 Survival

	Control	TRV027
Alive		
Dead		
Lost to follow-up		

Table 10 FAS Efficacy and exploratory parameters

	Control			TRV027		
	Day 1 [N=] Median (range)	Day 3 [N=] Median (range)	Difference D3 – D1	Day 1 [N=] Median (range)	Day 3 [N=] Median (range)	Difference D3 – D1
D-dimer						
Platelets						
aPTT						
INR						
Fibrinogen						

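### SAP text plans marker comparisons on Days 3, 5 and 8 by unadjusted differences, but the marker tables stop at Day 3; reconcile them and use one baseline-adjusted model per marker

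*SAP*

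**What the plan says.** **Text.** SAP 3.3: "Exploratory data variables will be measured at baseline and at days 3,5 and 8", with a reference to Tables 9 and 11. For each variable it takes the patient's difference from baseline, gives a mean and 95% confidence interval per arm, and compares the arms with a parametric or non-parametric test. SAP 1.3, under its secondary endpoints, says that changes "from day 1 to day 3, day 5, day 8 for exploratory variables will be investigated". Protocol 3.1 calls these variables exploratory. Neither document names a model across days, a summary over days, a baseline covariate or a multiplicity rule for them.

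**Tables.** "Table 10 FAS Efficacy and exploratory parameters" has 14 laboratory rows, including D-dimer, with columns for Day 1, Day 3 and their difference. Table 11 has two rows (inotrope requirement, D-dimer response), also for Days 1 and 3. Table 9 is Day 30 survival. Table 12 reaches Day 5, but for vital signs only and without columns by arm.

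**Sampling and population.** Protocol 3: "If discharge is planned for day 6 or 7 the day 8 blood tests can be taken on the day of discharge". The SAP does not say how such a sample is analysed. SAP 2.2 limits the Full Analysis Set (FAS) to patients who had the full course, and SAP 2.4 covers missing data only for the primary endpoint.

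**The concern.** The secondary objective, on dysregulation of other systems, rests on these markers. As written, a reader cannot tell whether Day 5 and Day 8 results will be analysed and reported at all, because the text says yes and the tables have no place for them.

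If they are analysed, the natural reading is a separate two-group test for each marker on each day. That uses neither the baseline value as a covariate nor the correlation between days, and it produces many tests with no stated rule for reading them. Later days also lose patients: Protocol 4.4 expects many to progress to organ failure or death, and SAP Table 2 counts doses missed through discharge and death.

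**Working it through.** **1. The plan's own figure.** SAP 1.5: "The sample size (30 each group) provides 80% power (alpha 0.05) to detect a 30% reduction in the D-dimer level". Protocol 7 gives the same numbers for a 30% change. No SD is given, so the figure can be neither confirmed nor refuted. On the log scale the effect is |ln 0.7| = 0.357. Solving for the SD of the change that gives 80% power with 30 per arm, two-sided 0.05, yields 0.485 by the t-test (0.493 by the normal approximation). By the normal approximation, other SDs would need: 0.4, 20 per arm; 0.6, 45; 1.0, 124. I use 0.485 below only because it matches the stated power.

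**2. Number of tests.**
- Text governs: 14 markers × 3 days = 42, less primary D-dimer at Day 3 = 41. Expected false positives if no effect exists: 41 × 0.05 = 2.05. Chance of at least one: 1 − 0.95^41 = 87.8% if independent, and about 53-84% under assumed correlations of 0.5-0.8 within a marker and 0-0.5 between markers.
- Adding inotrope requirement, GCS and SOFA on three days: 41 + 9 = 50.
- Tables govern: 14 − 1 = 13 exploratory marker tests (15 with the two rows of Table 11). Expected false positives for the 13: 0.65.
- One averaged test per marker: 14, including D-dimer. Expected false positives: 14 × 0.05 = 0.70.

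**3. Variance.** Assume equal correlation ρ between all days, complete data and unit variance on each day.
- Single-day change score: 2(1 − ρ), which is 1.00 at ρ = 0.5 and 0.40 at ρ = 0.8.
- Single day, baseline-adjusted: 1 − ρ², which is 0.75 and 0.36.
- Three-day average, baseline-adjusted: (1 + 2ρ)/3 − ρ², which is 0.417 and 0.227.

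Adjusted average against adjusted single day: 0.417/0.75 = 0.556, and 0.227/0.36 = 0.630. Adjusted average against the planned change score: 0.417/1.00 = 0.42, and 0.227/0.40 = 0.57.

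**4. Power, using D-dimer as an illustration.** Effect 0.357, 30 per arm, SD of a single-day change 0.485, with the SD of each other estimate scaled by the square root of its variance ratio to the change score.

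| Comparison | ρ = 0.5 | ρ = 0.8 |
|---|---|---|
| Single-day change score | 80% | 80% |
| Single day, baseline-adjusted | 90% | 84% |
| Three-day average, adjusted, constant effect | 99% | 96% |
| Three-day average, adjusted, effect halved on Days 5 and 8 | 82% | 70% |

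In the last row the mean effect is (1 + 0.5 + 0.5)/3 = 2/3 of 0.357, or 0.238.

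**The case against.** The strongest reply is that these are exploratory variables in a 60-patient experimental-medicine study, so about two chance findings in 41 harm nothing if the results are labelled hypothesis-generating. That is fair. It limits the weight of the point but does not remove the mismatch between text and tables.

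The gain is also conditional. Much of it comes from baseline adjustment and not from the extra days: adjustment alone takes 80% to 90-84%. If the effect fades after Day 3, the average can do worse than an adjusted Day 3 comparison, and at ρ = 0.8 worse than the plain change score. The documents give no SD, correlation or dropout rate with which to choose between these cases.

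A reader might infer several stronger things that the documents do not support:
- That Day 5 and Day 8 data are wasted and that 41 tests result. These belong to incompatible readings: under the text the data are analysed, and under the tables there are 13 exploratory marker tests.
- That the plan ignores D-dimer after Day 3. Protocol 3.1 lists it as exploratory on Days 1, 3, 5 and 8. What is missing is a single analysis of the whole course.
- That the primary test's error rate or power is affected. Day 3 D-dimer is a separate, named primary endpoint.
- That a mixed model cures dropout. Fitted to full-course patients only, it cannot recover those whom SAP 2.2 excludes, and missing at random is doubtful for death and discharge. The discharge-day sample in Protocol 3 already reduces Day 8 losses.
- That modelling by itself cuts the number of comparisons. Testing 14 averages and 42 by-day effects would make 56. The count falls only if the by-day effects are descriptive.

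**Conclusion.** The point holds as a low-cost improvement. The firm finding is internal: SAP 1.3 and 3.3 plan Days 3, 5 and 8, Tables 10 and 11 provide for Days 1 and 3, and the Table 9 reference is wrong. Depending on which governs, the result is either 41 unadjusted laboratory-marker tests (about 2 expected false positives) or unreported Day 5 and Day 8 results with 13 exploratory marker tests. That each day is tested separately is the natural reading of SAP 3.3, though the SAP does not say so.

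The precision gain is a best case that rests on equal correlation, no missing data and a constant effect. The 99-96% power figure illustrates the method on D-dimer. It is not a forecast for the other markers, for which the documents give nothing to calculate from.

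**What to change.** - In SAP 3.3, fit one mixed model per continuous marker, on the log scale where skewed, with baseline value, age group (the randomisation factor), day, treatment and treatment × day. Use the actual sampling day for Day 8 samples drawn early at discharge, and state how it enters the model.
- Include all randomised patients with a post-baseline value, not only those with the full course.
- Make the Days 3-8 average the single test per marker. Give by-day effects with 95% confidence intervals as descriptive. Label all of it hypothesis-generating.
- Add Days 5 and 8 to Tables 10 and 11, and correct the Table 9 reference in SAP 3.3.
- Keep Day 3 D-dimer as the primary endpoint.
- Report deaths and discharges by arm and day beside the model results.

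The cost is SAP wording, wider tables and modest programming, with no extra blood sample, visit or patient. The price in assumptions is missing at random, which the SAP should state openly. The change should be dated before the arms are compared.

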3.4 Safety data

Adverse events (AE) will be summarised by severity (NCI-CTCAE v4.03), classification, expectedness and relationship to the study drug (Table 3) and also described per patient for each treatment groups (Tables 4 and 5), while serious adverse events (SAE) will be summarised by SAE reason, severity, and causal relationship to study drug (Table 6). The details of each SAE will also be listed with the respective SAE term and outcome (Tables 7 and 8).

3.5 Drug Compliance

Drug compliance will be determined using data entered on to Redcap to calculate patient drug compliance. Number and duration of dose interruptions will be reported for each patient and compliance reported as the percentage of dose completion (Table 2). Although patients may receive up to 7 days infusion, for the primary endpoint, 72hrs infusion will be considered 100%.

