3.1 STUDY OUTCOME MEASURES

Primary Endpoint

- Mean change from baseline D-dimer at day 1 to day 3 post randomisation

Exploratory Endpoints

- Assessed on days 1, 3, 5, and 8
 - Markers of dysregulation of coagulation system, e.g.
 - D-dimer, Coagulation profile
 - Markers of dysregulation of RAS, e.g.
 - Renin mass and activity (Day 1 only)
 - Markers of dysregulation of other systems, e.g.
 - SOFA score ((Pa/SaO₂)/FiO₂, GCS, Total bilirubin, platelets, creatinine, BP and inotrope requirement).

- Markers of dysregulation of the endocrine system
 - BNP, Troponin, Ferritin, LDH, Haptoglobin
 - Glucose
- Markers of Inflammation (i.e. Bacterial Sepsis)
 - Pro-calcitonin

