2.2 Definition of population for analysis

The population for analysis will be the Full Analysis Set (FAS), which consists of all patients who received the full course of TRV027 or placebo. Patients who received at least 1 dose of TRV027 or placebo, but did not complete 3 days of infusion (Incomplete Analysis Set (IAS)) will be included in the baseline data set and summarised with descriptive statistics.

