3.2 Efficacy data

DDimer levels will be measured at baseline and at 3 days. Differences in DDimer will be calculated for each patient, enabling an estimate of the mean difference and 95% confidence interval to be calculated for each treatment arm. The differences for the treatment groups will be compared using parametric or non-parametric tests as appropriate (Table 10). In addition, a 30% reduction in DDimer will be considered a response, and so the proportions responding (with 95% CI) will be calculated, and compared for the two groups (Table 11). The results of these two analyses will provide sufficient evidence to differentiate between statistical and clinical significance.

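### Infusion received after the Day 3 D-dimer sample can decide who enters the primary comparison, because the SAP's 3-day and 72-hour cuts outlast a sample nominally due at about 48 hours

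*SAP*

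**What the plan says.** The primary endpoint in Protocol 3.1 is "Mean change from baseline D-dimer at day 1 to day 3 post randomisation". SAP 3.2 describes the timing differently: "DDimer levels will be measured at baseline and at 3 days".

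SAP 2.2 defines the analysis population as the Full Analysis Set (FAS), meaning patients who received the full course. It does not say whether that is 72 hours or 7 days. Patients who started but "did not complete 3 days of infusion" form the Incomplete Analysis Set (IAS), which gets baseline and descriptive summaries only. SAP Table 10, which holds the D-dimer comparison, is labelled FAS.

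SAP 3.5 acknowledges that infusion may last up to 7 days, but says that "for the primary endpoint, 72hrs infusion will be considered 100" per cent. The resulting percentage is reported in SAP Table 2.

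Two other places point the other way. SAP 2.5 keeps withdrawn patients in the final analysis, and its reasons for withdrawal include toxicity, death and patient decision. Protocol 8.2 keeps patients who are switched to alternative treatment in the study for data analysis.

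**The concern.** A condition for entering a primary analysis set should not depend on what happens after the primary outcome has been measured. If the Day 3 sample is drawn at about 48 hours, infusion between then and 72 hours cannot affect it. A patient's stopping in that interval can, however, reflect how the patient is doing. Protocol 4.4 expects many patients to progress to organ failure, intensive care or death. SAP Table 2 has rows for doses missed through discharge and death. Protocol 1.3 reports an earlier infusion stopped for hypotension.

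If stopping is related to both arm and D-dimer, the patients left in the FAS are no longer comparable as randomised. With 30 per arm, a few such exclusions could matter.

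**Working it through.** **Inputs**

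- Start: Day 1 procedures "include a venous blood test prior to commencing an intravenous infusion" (Protocol 3), so Day 1 is taken as 0 h.
- Later samples: "Venous blood tests will be repeated at days 3, 5 and 8" (Protocol 3).
- Length: "The infusions will continue for 7 days" (Protocol 3), which is 7 × 24 = 168 h. Protocol Table 1 marks infusion on Days 1 to 8.
- Monitoring: "Once the infusion has finished, the subjects will remain in hospital for a further 24 hours" (Protocol 3). Protocol Table 1 runs vital signs to Day 9.
- Yardstick: 72 h (SAP 3.5).

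**Step 1: when is Day 3?** Elapsed hours = (study day − 1) × 24. Two anchors test this rule. The infusion ends at Day 8 = 7 × 24 = 168 h, and monitoring ends at Day 9 = 8 × 24 = 192 h = 168 + 24. Both fit Protocol Table 1. Day 3 is then 2 × 24 = 48 h, and 72 h is Day 4. The SAP's 72 h is reproduced as 3 × 24 only if SAP 3.2 is read as three elapsed days. It is not reproduced from the Day 3 column of Protocol Table 1.

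**Step 2: how firm is 48 h?** With calendar days and no visit window, a Day 3 draw could fall anywhere from about 24 h (late start, early draw) to about 72 h (early start, late draw). It reaches 72 h only at the extreme.

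**Step 3: what does the 72 h score measure?** Hours are counted within the first 72, and the sample is taken at the nominal 48 h.

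| Infusion pattern | SAP score | Exposure before sample |
|---|---|---|
| Stops at 36 h | 36/72 = 50% | 36/48 = 75% |
| Stops at 48 h | 48/72 = 66.7% | 48/48 = 100% |
| Stops at 60 h | 60/72 = 83.3% | 48/48 = 100% |
| Off from 24 to 48 h, then on to 72 h | 48/72 = 66.7% | 24/48 = 50% |
| No gap, 72 h or longer | 72/72 = 100% | 48/48 = 100% |

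One third of the denominator (24/72) lies after the sample. The second and fourth rows share a score, although one patient had twice the relevant exposure of the other.

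**Step 4: who can be left out?** If 3 days means 72 h, anyone stopping between 48 and 72 h falls in the IAS. If full course means 7 days, anyone stopping between 48 and 168 h is outside the FAS, and those stopping between 72 and 168 h fit neither definition.

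**Step 5: how many?** The documents give no stopping rate. As an illustration only, assume a constant daily stopping risk p. Of 60 patients, the expected number stopping in each window is 60 × [(1 − p)² − (1 − p)³] for 48–72 h and 60 × [(1 − p)² − (1 − p)⁷] for 48–168 h.

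| Assumed p | 48–72 h | 48–168 h |
|---|---|---|
| 2% | 1.2 | 5.5 |
| 5% | 2.7 | 12.2 |
| 10% | 4.9 | 19.9 |
| 15% | 6.5 | 24.1 |

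**The case against.** The strongest reply is that the SAP is coherent if its terms all mean elapsed time: a sample at 3 days, a cut at 3 days of infusion, and a 72 h yardstick. The endpoint's post-randomisation wording can be read that way too. This stands as a possible intention. It does not agree with the Day 3 column of Protocol Table 1, and SAP Table 10 itself labels the columns Day 1 and Day 3. The texts need reconciling on either reading.

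The 3-day cut in SAP 2.2 might also mean infusion on calendar Days 1, 2 and 3. That would shrink the problem at the IAS boundary, and SAP 2.2 does not rule it out. SAP 3.5, however, counts in hours, and a 7-day meaning of full course would enlarge the problem.

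SAP 2.5 may be taken to rescue these patients. It does conflict with SAP 2.2, but nothing says which section prevails. Stopping because of discharge is also not among its listed reasons.

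On differential stopping, Protocol 1.3 reports no difference from placebo in events leading to discontinuation in the 621-patient acute heart failure study. That is fair evidence against a large arm difference through adverse events. It comes from another disease and infusions of 48–96 hours, and it does not cover stopping through discharge or deterioration in COVID-19.

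Three stronger inferences are tempting but unsupported:

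- That the 72 h percentage itself excludes patients. It does not. It feeds a descriptive table, and the sorting comes from SAP 2.2.
- That compliance can exceed 100% over a full course, or that hours after 72 can make up for an early gap. Both need an uncapped count. The natural reading of SAP 3.5 is a target over the first 72 hours.
- That a patient stopped at 60 hours is certainly excluded. This depends on what 3 days means.

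**Conclusion.** The point holds on the nominal schedule, with medium confidence. As written, SAP 2.2 can remove patients with a valid on-treatment Day 3 D-dimer from the primary comparison because of what happens after that sample. The window is about 48 to 72 hours, or up to 168 hours if full course means 7 days. The compliance mismatch (67% for a patient fully exposed up to the sample) is descriptive, and minor taken alone.

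The conclusion assumes that Day 1 is 0 h and that the draw is near 48 h. Neither is stated as a clock time. A reader might infer that the primary result is shown to be biased. The documents do not support that: the bias is possible, but the number affected and its direction cannot be computed, and the counts in the working rest on assumed stopping rates.

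**What to change.** 1. Reconcile the timing terms across protocol and SAP: Day 3, the SAP's 3 days for the sample, its 3 days of infusion, its 72 hours and its full course. State the intended time and window of the Day 3 draw.
2. Define the primary analysis set as every randomised and treated patient with Day 1 and Day 3 D-dimer, whatever infusion followed the draw. This agrees with SAP 2.5 and Protocol 8.2. Say explicitly which rule governs if sections differ.
3. Score primary-endpoint compliance as hours infused from start to the Day 3 draw, divided by hours from start to that draw. Use the actual draw time if it is recorded and the nominal time otherwise.
4. Report compliance over the 7 days separately, against 168 hours.

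The cost is minor SAP rewording. SAP 3.5 already plans to report the number and duration of interruptions. The documents do not say that the clock time of the Day 3 draw is captured, so that needs confirming. These changes concern analysis definitions only, not how long anyone is infused.
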